13.0 DATA REPORTING/REGULATORY CONSIDERATIONS

Adverse event lists, guidelines, and instructions for AE reporting can be found in Section 8.0 (Adverse Events: List and Reporting Requirements).

13.1 Data Reporting

The OnCore Database will be utilized, as required by the Case Comprehensive Cancer Center, to provide data collection for both accrual entry and trial data management. OnCore is a Clinical Trials Management System housed on secure servers maintained at Case Western Reserve University. OnCore properly used is compliant with Title 21 CFR Part 11. Access to data through OnCore is restricted by user accounts and assigned roles. Once logged into the OnCore system with a user ID and

password, OnCore defines roles for each user which limits access to appropriate data. User information and password can be obtained by contacting the OnCore Administrator at [contact].

OnCore is designed with the capability for study setup, activation, tracking, reporting, data monitoring and review, and eligibility verification. This study will utilize electronic Case Report Form completion in the OnCore database. A calendar of events and required forms are available in OnCore.

13.2 Regulatory Considerations

The study will be conducted in compliance with ICH guidelines and with all applicable federal (including 21 CFR parts 56 & 50), state or local laws.

13.2.1 Written Informed Consent

Provision of written informed consent must be obtained prior to any study-related procedures. The Principal Investigator will ensure that the subject is given full and adequate oral and written information about the nature, purpose, possible risks and benefits of the study as well as the subject's financial responsibility. Subjects will also be notified that they are free to discontinue from the study at any time. The subject will be given the opportunity to ask questions and allowed time to consider the information provided.

The original, signed written Informed Consent Form will be kept with the Research Chart in conformance with the institution's standard operating procedures. A copy of the signed written Informed Consent Form will be given to the subject.

Withdrawal of consent: Subjects may choose to discontinue their participation in the study at any time by notifying the PI. They will be asked to send a written letter to the PI listed on the informed consent. No further research data will be obtained nor clinical data entered into the research database. Data gathered until the time of withdrawal will be maintained.

Illiterate subjects: In the event that illiterate individuals who understand English present themselves as potential study participants and meet all inclusion/exclusion criteria, the consent form will be read to that individual in the presence of a witness and all questions answered. The study participant will sign the consent document by "making their mark" in the signature space. Both the person obtaining the consent (either the PI or his/her official delegate) and the witness will co-sign and date the consent form, noting that the informed consent process has taken place.

Non-English speaking patients, house staff and students, medical students on a clerkship, and employees related to study personnel or who work for any study personnel, and members of the study team are not eligible to participate in this study as a subject.

13.2.2 Subject Data Protection

In accordance with the Health Information Portability and Accountability Act (HIPAA), each subject will sign an authorization to release medical information to the sponsor and/or allow the sponsor, a regulatory authority, or Institutional Review Board access to subject's medical information that includes all hospital records relevant to the study, including subjects' medical history.

All data will be recorded in patient specific study binders. These binders will be kept in a locked room only accessible to research personnel. This data will then be transferred to an electronic database stored on the UHCMC secure drive that will be password protected and only accessible to research personnel. The research team, authorized UH personnel, the study sponsor (if applicable), and regulatory entities such as the Food and Drug Administration (FDA) and the Office of Human Research Protections (OHRP), may have access to the study records to protect the subject's safety

and welfare. Any information derived from this research project that personally identifies the subject will not be voluntarily released or disclosed by these entities without a separate consent, except as specifically required by law. Research records provided to authorized, non-UH entities will not contain identifiable information about the subject. Publications and/or presentations that result from this study will not include identifiable information.

Digital photographs of the wound will be taken at each visit. The digital files will be stored on the UHCMC secure drive that only research personnel will have access to.

13.2.3 Accessing Electronic Medical Records for University Hospitals Health System
Not applicable

13.2.4 Retention of Records

The Principal Investigator at UHCMC supervises the retention of all documentation of adverse events, records of study drug receipt and dispensation, and all IRB correspondence for as long as needed to comply with national and international regulations. No records will be destroyed until the Principal Investigator confirms destruction is permitted.

13.2.5 Audits and Inspections

Authorized representatives of the sponsor, a regulatory authority, an Independent Ethics Committee (IEC) or an Institutional Review Board (IRB) may visit the study site to perform audits or inspections, including source data verification. The purpose of an audit or inspection is to systematically and independently examine all study-related activities and documents to determine whether these activities were conducted, and data were recorded, analyzed, and accurately reported according to the protocol, Good Clinical Practice (GCP), guidelines of the International Conference on Harmonization (ICH), and any applicable regulatory requirements.

13.2.6 Data Safety and Monitoring Plan

This protocol will adhere to the policies of the Case Comprehensive Cancer Center Data and Safety Monitoring Plan in accordance with NCI regulations.

13.2.7 Multicenter Guidelines

Responsibility of the Coordinating Center

- The Coordinating Center is responsible for the coordination, development, submission, and approval of the protocol as well as its subsequent amendments. The protocol must not be rewritten or modified by anyone other than the Coordinating Center. There will be only one version of the protocol, and each participating institution will use that document. The Coordinating Center is responsible for assuring that all participating institutions are using the correct version of the protocol.
- The Coordinating Center is responsible for the overall conduct of the study at all participating institutions and for monitoring its progress. All reporting requirements are the responsibility of the Protocol Chair.
- The Coordinating Center is responsible for the timely review of Adverse Events (AE) to assure safety of the patients.
- The Coordinating Center will be responsible for the review of and timely submission of data for study analysis.
- Each participating institution will have an appropriate assurance on file with the Office for Human Research Protection (OHRP). The Coordinating Center is responsible for assuring that each participating institution has an OHRP assurance and must maintain copies of IRB approvals from each participating site.
- Prior to the activation of the protocol at each participating institution, an OHRP form 310 (documentation of IRB approval) must be submitted to the Coordinating Center.

- The Coordinating Center is responsible for central patient registration. The Coordinating Center is responsible for assuring that IRB approval has been obtained at each participating site prior to the first patient registration from that site.
- The Coordinating Center is responsible for the preparation of all submitted data for review.
- The Coordinating Center will maintain documentation of AE reports.
- Audits may be accomplished in one of two ways: (1) source documents and research records for selected patients are brought from participating sites to the Coordinating Center for audit, or (2) selected patient records may be audited on-site at participating sites. If the funding or regulatory agency chooses to have an audit at the Coordinating Center, then the Coordinating Center is responsible for having all source documents, research records, all IRB approval documents, Drug Accountability Record forms, patient registration lists, response assessments scans, x-rays, etc. available for the audit.

Agent Ordering

- Except in very unusual circumstances, each participating institution will order Dysport directly from Medicis. Investigational agents may be ordered by a participating site only after the initial IRB approval for the site has been forwarded by the Coordinating Center to Medicis.

14.0 STATISTICAL CONSIDERATIONS

To quantify the improvement in scar appearance, we propose the use of two well-established methods of measurement: The Visual Analogue Scale (VAS) and the Patient and Observer Scar Assessment Scale (POSAS)^{6,7}. The VAS will be used as the primary end point. It consists of a 10 point scale to assess global scar assessment. Scar photographic images are assessed by independent physicians, and previous studies have shown very high intrarater consistency. The POSAS consists of two numeric scales. One scale is completed by the patients, the other by the clinician. This scale is different than previous scales because it takes the patient's input into consideration. It has good internal consistency and interobserver reliability.^{8,9}

14.1 Visual Analog Scale: This is a 10 point scale to assess global scar assessment. VAS has been used in previous studies to assess cosmetic outcome of scars. In this study, we plan to evaluate the efficacy of using aboBTX-A to improve wound healing prior to Mohs micrographic surgery and reconstruction for skin cancer as measured by the Visual Analogue Scale (VAS) at 6 weeks post surgery as the primary endpoint.

- 14.1.1** Meaningful clinically important difference: Using the data from 2 previously published clinical trials, Quinn et al⁷ reported that the minimal clinically important difference on the VAS cosmesis scale is 1.5 on a 10 point VAS¹¹
- 14.1.2** Sample size calculation: Prior authors have reported a pooled SD of 1.4 and 2.2 among VAS scores for surgical scars, yielding an effect size (mean difference/SD) of 0.7 to 1.1. A sample size of 20 patients per treatment group would provide an 80% chance (statistical power) of detecting an effect size of 1.0, using a two-sided t-test, with a type I error level of 5%. Assuming a 5-10% dropout rate with follow-up visit and given the efficiency of the 2-sample *t* test relative to the Wilcoxon rank sum test is 95%, a total of 25 patients will be enrolled per group.
- 14.1.3** Data Analysis: The VAS ratings at 6 weeks and at 6 months for each patient will be based on the average of all four physician scores. The average of the VAS scores will then be compared between the 2 treatment groups using the Wilcoxon rank sum test. All calculated *P* values are 2-sided, and $P < 0.5$ is considered statistically significant.
- 14.1.4** Patient Accrual is anticipated that at least 10 subjects will be enrolled in the first year at UHCMC.

[figure not shown]
14.2 Patient and Observer Scar Assessment Scale: This scale will allow us to assess the patient and observer's opinion of his/her scar as a secondary endpoints. In comparison to the VAS, this scale takes the patient's input into consideration. In addition, multiple parameters are evaluated including vascularity, pigmentation, thickness, and surface area. Parameters. Prior studies have shown good internal consistency and interobserver reliability⁸⁻¹⁰. The average PSAS and OSAS scores for each parameter will be compared between the 2 treatment groups using the Wilcoxon rank sum test. All calculated *P* values are 2-sided, and *P*<0.5 is considered statistically significant.

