3.0 STUDY DESIGN

3.1 Study Design including dose escalation/cohorts/subject numbers

This is a 6 month, prospective, multicenter, double-blinded, randomized, placebo-controlled study. A total of 40 male or female healthy volunteers, 20 in each arm, will be enrolled. Up to 10 more patients can be enrolled to account for patient drop-out. Subjects will all undergo Mohs micrographic surgical removal of a skin cancer lesion on the forehead followed by reconstruction. Subjects will be randomized to receive either aboBTX-A injection or placebo injection in the frontalis, procerus, and corrugator muscles prior to reconstruction. Photographs, POSAS, and clinical assessments will be taken immediately after initial wound closure, at 1 week follow-up, at 6 weeks follow-up, and at 6 months follow-up. Adverse events will also be reviewed at each study visit. After the completion of the study, the photographs will be assessed (blinded as to the patient identifiers) using a 10 cm visual analog scale (VAS). The first few photographs will be evaluated by the surgeons together to calibrate the VAS and ensure inter-reliability.

Procedure	Visit 1: Screening & Dysport Administration	Visit 2: Op Visit	Visit 3: 1 wk f/u	Visit 4: 6 wk f/u	Visit 5: 6 month f/u
Informed Consent	X				
Pre-op Evaluation	X				
Injection of Dysport or Placebo	X				
Adverse Events	X	X	X	X	X
Medical/Medication History	X	X	X	X	X
Photography	X	X	X	X	X
Skin Evaluation		X	X	X	X
Urine Pregnancy Test	X				X
Assessments					
Physician VAS				X	X
Patient POSAS		X	X	X	X
Physician POSAS		X	X	X	X
Patient survey					X

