3.2 Number of subjects

Subjects for this study will be recruited from up to five clinical sites. A total of forty healthy evaluable subjects will participate in this study. Up to fifty subjects will be enrolled to account for projected dropout. It is anticipated that at least 10 subjects will be enrolled in the first year at UHCCM. An evaluable subject is one who has passed the inclusion and exclusion criteria; given informed consent; received and followed the treatment schedule, and has been adequately followed to establish valid endpoints of efficacy and tolerance.

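### Section 14.1.2 states 80% power for an effect size of 1.0 with 20 patients per group, but its own inputs give 87% (t-test)

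*Combined protocol and SAP*

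**What the plan says.** Section 14.1.2 takes a minimal important difference of 1.5 points (section 14.1.1) and two published SDs for scar VAS scores, 1.4 and 2.2, "yielding an effect size (mean difference/SD) of 0.7 to 1.1". It then gives the only power statement in the plan: "A sample size of 20 patients per treatment group would provide an 80% chance (statistical power) of detecting an effect size of 1.0". The same sentence sets the test behind that figure: a t-test, two-sided, at the 5% level.

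The next sentence of 14.1.2 brings in 5-10% dropout and a 95% relative efficiency between the t-test and the Wilcoxon test, and concludes that "a total of 25 patients will be enrolled per group". Section 14.1.3 names the Wilcoxon rank sum test as the analysis of the rater-averaged VAS.

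Sections 3.1 and 3.2 also use 20 per arm as the base: "A total of 40 male or female healthy volunteers, 20 in each arm, will be enrolled" and "A total of forty healthy evaluable subjects will participate in this study". Both treat the further 10 patients as cover for dropout. Section 3.3 adds that a patient who withdraws is replaced in the same arm.

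**The concern.** The power sentence names the group size, the effect size, the test, its sidedness and its error level. Because the effect is expressed in SD units, no SD is needed, and one power value follows. A familiar rule of thumb is about 16 or 17 per group for 80% power at an effect of one SD, so 20 per group should give clearly more than 80%.

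This is the plan's only power statement, and it concerns the primary endpoint. As written, it tells the reader that 1.0 SD is the difference the trial can detect with 80% power. A reader who tries to reproduce it cannot, and anyone who later judges a null result against it would be using the wrong detectable effect.

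**Working it through.** **Inputs, all from section 14.1.2.** n = 20 per group; effect size d = 1.0; two-sided two-sample t-test; alpha = 0.05; stated power 80%. Equal allocation is confirmed by section 3.1. Section 14.1.3 prints a different significance threshold. That is a separate matter, and this check uses the 5% of 14.1.2.

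**1. Trying to reproduce the stated 80%.** Power is the probability that a noncentral t variable exceeds the critical value in absolute size.

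- Degrees of freedom: 2 × 20 − 2 = 38; two-sided 5% critical value 2.024.
- Noncentrality: d × √(n/2) = 1.0 × √10 = 3.162.
- Power: **86.9%**.
- Cross-check by normal approximation: Φ(3.162 − 1.960) = Φ(1.202) = 88.5%. This runs slightly high, as expected in small samples.

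The stated figure is about 7 points too low.

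**2. What would give 80%?**

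| Change made | Power |
|---|---|
| d = 0.91, n = 20 | 80.0% |
| d = 1.0, n = 17 | 80.7% |
| d = 1.0, n = 16 | 78.1% |
| d = 1.0, n = 19 (5% dropout taken out of 20) | 85.1% |
| d = 1.0, n = 18 (10% dropout taken out of 20) | 83.0% |
| d = 1.0, n = 20, one-sided 5% | 92.8% |
| d = 1.0, n = 20, two-sided 1% | 67.3% |

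No variant that keeps both 20 per group and an effect size of 1.0 returns 80%.

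**3. The planned Wilcoxon test.** Using the plan's own 95% efficiency, the effective group size is 20 × 0.95 = 19, and the t-test power is 85.1%. Direct simulation of the rank sum test with exact critical values, normal data and a shift of 1 SD gives about 85%. Using the planned test therefore does not account for the gap either.

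**4. The allowances.** Applied after the 20, as the text does:

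- 20 / (0.95 × 0.95) = 22.2 per group at 5% dropout;
- 20 / (0.95 × 0.90) = 23.4 per group at 10% dropout.

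Both are below 25, so the step from 20 to 25 is sufficient and is not what is wrong.

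**5. The plan's own range, t-test, 20 per group.**

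| Effect size | Power |
|---|---|
| 0.7 | 58% |
| 0.91 | 80% |
| 1.0 | 87% |
| 1.1 | 92% |

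The ends of the range are rounded in the plan. Unrounded, 1.5/2.2 = 0.68 gives 56%, and 1.5/1.4 = 1.07 gives 91%.

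**The case against.** **The consequence is close to nil.** At the effect size the plan names, 20 per group does better than claimed. Read as a minimum, which is how planning statements are often meant, the sentence would be true. This stands as a reason to rate the point minor. It does not make the sentence right: the wording gives 80% as the power, not as a floor.

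**The 20 may already contain the allowances.** Since 17 per group gives 80.7%, and 17 / (0.95 × 0.90) = 19.9, the number could have arisen that way. A reader might go on to infer that the allowances were counted twice and that 25 is too many. The documents do not support this. The 80% is attached to 20 patients and a t-test, the allowances are introduced afterwards, and sections 3.1 and 3.2 treat 20 per arm as the base. It remains a possible origin for a drafting slip and nothing more.

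**Power at 0.7 is not an arithmetic error.** This is correct. The plan prints its range openly and chooses 1.0 within it. A reader might infer from 58% that the trial is underpowered, or from 87% that it is oversized. Neither follows: the plan sizes the trial for 1.0, and at 1.0 it exceeds its 80% target. The end-of-range figures are useful only as context, and adding them is optional.

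**The Wilcoxon figure depends on the shape of the data.** This also stands. With a shift of 1 SD and 20 per group, simulation gives about 85% for normal data, 81% for uniform data and 91% for a t distribution with 5 degrees of freedom. The last two shapes are illustrative assumptions, but the VAS is bounded (Appendix 1 runs from 1 to 10), so any Wilcoxon figure should carry its normality assumption. All three still lie above 80%.

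**Conclusion.** The point holds as a minor arithmetic error. With the inputs printed in section 14.1.2, t-test power is 87% rather than 80%. The effect size that 20 per group can detect with 80% t-test power is 0.91 rather than 1.0.

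The t-test figures rest only on the printed inputs and the usual t-test assumptions; no SD or outside source is involved. The figure of about 85% for the planned Wilcoxon test additionally assumes normally distributed scores. All figures take 20 evaluable patients per group, consistent with the forty evaluable subjects of section 3.2 and the same-arm replacement of section 3.3.

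The error understates power at 1.0, so it does not weaken the trial for the effect it was sized on. Nor is it an argument for fewer patients, given that t-test power at the low end of the plan's own range is 58%.

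**What to change.** Replace the power sentence in section 14.1.2 with:

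*With 20 evaluable patients per group and a two-sided 5% t-test, power is 87% for an effect size of 1.0 (about 85% for the Wilcoxon rank sum test, assuming normally distributed scores); 80% t-test power corresponds to an effect size of 0.91.*

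Optionally add:

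*Over the range 0.7 to 1.1, t-test power with 20 per group runs from 58% to 92%.*

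The cost is a wording change in one section. No extra patients and no change of test or enrolment target are asked for. If the optional sentence is used, the only drawback is that the plan discloses a less favourable power at the low end of its range.

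### The written significance threshold is P < 0.5, ten times the 5% type I error used to size the trial

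*Combined protocol and SAP*

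**What the plan says.** Section 14.1.2 (Sample size calculation) sizes the trial "using a two-sided t-test, with a type I error level of 5" percent. The design alpha is therefore 0.05, two-sided. On power, the same item states: "A sample size of 20 patients per treatment group would provide an 80% chance (statistical power) of detecting an effect size of 1.0".

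Section 14.1.3 (Data Analysis) averages four physicians' VAS ratings per patient at 6 weeks and at 6 months. The averages are then "compared between the 2 treatment groups using the Wilcoxon rank sum test". The decision rule is that P "values are 2-sided, and $P < 0.5$ is considered statistically significant". The 6-week comparison is the primary endpoint.

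Section 14.2 (POSAS) uses the same test for each parameter, and again P "values are 2-sided, and *P*<0.5 is considered statistically significant".

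No other section gives a P-value threshold, and none explains or overrides 0.5.

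**The concern.** Sections 14.1.2 and 14.1.3 are consecutive items of the same section and give values of alpha that differ by a factor of ten. The larger one sits in the sentence that decides whether the primary endpoint is met.

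Read literally, the trial would declare a difference between aboBTX-A and placebo about half the time when there is none. By symmetry, about a quarter of null trials would show a significant benefit and about a quarter a significant harm. A claim of efficacy made under that rule would carry almost no evidential weight.

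There is also a problem if nobody applies it literally. An analyst who uses 0.05 without an amendment departs from the prespecified rule, and the record would not show when the threshold was chosen.

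**Working it through.** **Inputs**
- Design alpha 0.05 two-sided, 20 per group, effect size 1.0, stated power 80% (14.1.2).
- SDs: "pooled SD of 1.4 and 2.2 among VAS scores for surgical scars, yielding an effect size (mean difference/SD) of 0.7 to 1.1" (14.1.2).
- Clinical benchmark: "the minimal clinically important difference on the VAS cosmesis scale is 1.5 on a 10 point VAS" (14.1.1).
- Written threshold 0.5, two-sided, Wilcoxon rank sum test (14.1.3 and 14.2).

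**Step 1. The plan's own power figure, and which alpha it came from.** The calculation is a two-sample t-test with df = 2n − 2 and noncentrality d × √(n/2). With d = 1.0 and n = 20, the noncentrality is 1.0 × √10 = 3.16 on 38 df.

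| Two-sided alpha | Power, 20 per group | n per group for 80% power |
|---|---|---|
| 0.05 | 86.9% | 17 |
| 0.5 | 99.3% | 5 |

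The stated 80% is not reproduced exactly. At alpha 0.05 the plan understates its power, which is a separate and conservative discrepancy. At alpha 0.5, 5 per group would have been enough, so 20 per group was not derived from 0.5.

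**Step 2. False-positive rate of the written rule.** The exact null distribution of the Wilcoxon rank sum statistic, 20 v 20 without ties, gives:

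| Rule | Exact size | Either single direction |
|---|---|---|
| P < 0.5 | 49.5% | 49.5/2 = 24.7% |
| P < 0.05 | 4.9% | 4.9/2 = 2.5% |

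Simulation of 20,000 null trials with normal data agrees: 50.0% and 5.2%. With all 25 per group analysed, the exact sizes are 48.8% and 4.9%.

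**Step 3. Smallest observed difference that would be significant.** A rank test has no fixed cut-off in mean difference, so this step uses the t-test as an approximation: critical difference in SD units = t(1 − α/2, 38 df) × √(2/20).

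- At 0.5: 0.681 × 0.316 = 0.215 SD. In VAS points: 0.215 × 1.4 = 0.30 and 0.215 × 2.2 = 0.47. Relative to 1.5 points: 20% and 32%.
- At 0.05: 2.024 × 0.316 = 0.640 SD. In VAS points: 0.640 × 1.4 = 0.90 and 0.640 × 2.2 = 1.41. Relative to 1.5 points: 60% and 94%.

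With 25 per group the critical differences are 0.19 SD and 0.57 SD.

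**Step 4. POSAS.** Section 14.2 does not say how many tests there are, so the count is an assumption. The expected number of false positives is the number of tests times alpha, whatever the correlation between items.

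| Reading | Tests | Expected at 0.5 | Expected at 0.05 |
|---|---|---|---|
| Four parameters named in 14.2, at weeks 1, 6 and 24 (Section 2.2) | 4 × 3 = 12 | 6 | 0.6 |
| All seven observer and seven patient items in Appendix 2, same visits | 14 × 3 = 42 | 21 | 2.1 |

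**Step 5. After correction.** With P < 0.05 the exact size (4.9%) matches the 5% in 14.1.2. Power at effect size 1.0 with 20 per group is 86.9% by t-test and about 85% by Wilcoxon (simulated).

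**The case against.** The strongest reply is that this is a typing error whose intended value is plain. The 5% stands in the item just before, step 1 shows that the sample size was not built on 0.5, and no competent analyst would apply 0.5. On that view, speaking of a 50% false-positive rate overstates a slip. The diagnosis is right and should be said openly: 0.05 was almost certainly meant. It does not dispose of the point, because the wrong value is the only decision threshold the plan contains and it governs the primary endpoint. Under Section 13.2.7 only the Coordinating Center may change the protocol, so sites and analysts cannot correct it themselves.

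A fault in reading the PDF can be considered. The value appears in two separate sections with different typography, so the loss of the same zero in both is unlikely.

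Two objections to the illustrative figures stand in part. The number of POSAS tests depends on what counts as a parameter and on which visits are analysed, and ties on 1-to-10 integer items can move the actual rates away from nominal. The critical differences are t-test approximations to a rank test. Neither affects the contradiction between the two alphas.

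**Conclusion.** The concern holds. The plan's written decision rule contradicts its own design alpha by a factor of ten, for the primary VAS comparison and for POSAS. Applied literally, it gives a type I error of about 50% per test (49.5% exact for the Wilcoxon test at 20 per arm, assuming no ties) instead of 5%. The contradiction rests on the text alone. The differences in VAS points assume 20 analysed patients per arm, the plan's SDs and the t approximation. The POSAS totals depend on the reading chosen. A typing error is the likely cause, but the correction must be made because the error lies in the success criterion for the primary endpoint.

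**What to change.** In Sections 14.1.3 and 14.2, replace 0.5 with 0.05, so that both agree with the two-sided 5% in Section 14.1.2. Issue this through the Coordinating Center as a dated amendment before unblinding, so that the threshold is on record ahead of the results.

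The cost is one inserted digit in each of two places, plus the amendment paperwork. Sample size, visits, assessments and the choice of test are unchanged.
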